## 8.8 LABORATORY ASSESSMENTS

The following lab measurements will be obtained (as part of the subject's medical record) and recorded per the study schedule of events:

- [REDACTED]

### **8.9 URINE PREGNANCY TEST**

Urine pregnancy test will be performed for females of child-bearing potential. The result must be documented on the source documents and in the eCRF. Subjects who are found to be pregnant during the screening period will be considered a screen failure. If pregnancy occurs during the course of the study, the subject will be withdrawn from the study and the pregnancy will be followed up to term for safety purposes. Relevant safety information collected after the study has completed will be reported as supplemental information.

### **8.10 ELECTROCARDIOGRAM (ECG)**

A standard 12-lead ECG will be performed per the site standard procedures. The following parameters will be recorded (as part of the subject's medical record) and recorded on the appropriate page of the CRF: ventricular rate (beats per minute), PR interval (msec), QRS interval (msec), QT interval (msec), and QTc interval (msec). Additionally, the Investigator will record the overall results of the ECG reading as either normal or abnormal, and if abnormal, as either "not clinically significant" or "clinically significant." If abnormalities are observed, each will be recorded. Each treatment-emergent abnormality that is clinically significant will be recorded as an AE. Each ECG should be signed by a physician.

### **8.11 COHORT ASSIGNMENT (PART 1 ONLY, SEQUENTIAL)**

In Phase I (Part 1) of the study, five (5) cohort dose levels will be tested sequentially by escalating AMTX-100 CF 1.1% application of treatable % BSA involvement at each cohort. Five (5) cohorts will be sequentially enrolled in the Part 1 of the study.

Site personnel will be notified about the cohort (dose level) escalation to the higher dose level cohort. Subjects will be assigned in the designated cohort (dose level) at the time of screening, using an Interactive Web Response System (IWRS) and site personnel will be trained on this system.

### 8.12 RANDOMIZATION (PART 2 ONLY)

In Phase II (Part 2) of the study, subjects will be randomized using a web-based randomization system at Visit 2 and site personnel will be trained on this system.

[REDACTED]

[REDACTED]

[REDACTED]

- | [REDACTED]
- | [REDACTED]
- | [REDACTED]
- | [REDACTED]
- | [REDACTED]
- | [REDACTED]
- | [REDACTED]

[REDACTED]

- | [REDACTED]
- | [REDACTED]
- | [REDACTED]
- | [REDACTED]

[REDACTED]

- | [REDACTED]
  - [REDACTED]
  - [REDACTED] [REDACTED] [REDACTED] [REDACTED] [REDACTED] [REDACTED] [REDACTED]
  - [REDACTED]
  - [REDACTED] [REDACTED] [REDACTED] [REDACTED] [REDACTED] [REDACTED] [REDACTED]
  - [REDACTED]

[REDACTED]

[REDACTED]

[REDACTED]						
[REDACTED]						
[REDACTED]						
[REDACTED]						
[REDACTED]						
[REDACTED]						
[REDACTED]						
[REDACTED]						

[REDACTED]

[REDACTED]

[REDACTED]

## 9 STATISTICAL CONSIDERATIONS

This section presents general information about statistical considerations and concepts such as randomization, covariates, statistical power, sample size, and a brief discussion on analysis methodology, as well as some data conventions. Detailed descriptions of the statistical analysis methods and data conventions will be included in a separate document; i.e., the Statistical Analysis Plan (SAP).

### 9.1 TREATMENT GROUPS

The Part 1 of this study is an open-label, dose escalation study of the safety and tolerability of topically applied AMTX-100 *CF* in adult patients with mild to moderate Atopic Dermatitis (AD). Five (5) cohorts will be sequentially enrolled in this Part 1 of the study. The description of the 5 cohorts is presented below in [Table 9-1](#).

[REDACTED]

[REDACTED]	[REDACTED]

The Part 2 of this study is a multi-center, double-blind, randomized, vehicle-controlled study of the safety and efficacy of topically applied AMTX-100 *CF3* in adult patients with Mild to Moderate Atopic Dermatitis (AD). The description of the treatment groups for this Part of the study is presented below in [Table 9-2](#).

**Table 9-2: Treatment Groups in Part 2**

Group	Description
Group A	AMTX-100 CF3 (1.1% w/w), topically applied twice a day for 28 consecutive days to all treatable AD affected areas
Group B	Placebo (Vehicle) (0% w/w), topically applied twice a day for 28 consecutive days to all treatable AD affected areas

### 9.2 DESCRIPTION OF STUDY OUTCOME MEASURES

#### 9.2.1 PHASE I (PART 1) STUDY OUTCOME MEASURES

**9.2.1.1 Primary Outcome Measure:**

- Maximum Tolerable Dose (MTD) by maximum percentage of BSA treated, by evaluation of dose-limiting toxicity (DLT) of AMTX-100 *CF* (1.1% w/w concentration) based on the safety profile

**9.2.1.2 Safety Outcome Measures:**

- Incidence of Treatment-Emergent Adverse Events (TEAE)
- Incidence of withdrawals from the study due to TEAEs
- Changes in study treatment application site reaction assessment
- Changes and shifts in laboratory measurements over time
- Changes in vital signs over time treatment

[REDACTED]

■ [REDACTED]

■ [REDACTED]

**9.2.2 PHASE II (PART 2) STUDY OUTCOME MEASURES**

**9.2.2.1 Primary Efficacy Outcome Measure:**

- Proportion of responder subjects at Day 28, defined as subjects with both Validated Investigator Global Assessment for Atopic Dermatitis (vIGA-AD™) score of 0 (clear) or 1 (almost clear) (on a 5-point scale) and a reduction of  $\geq 2$  points from baseline

Note: Subjects who receive rescue treatments will be considered non-responders

[REDACTED]

■ [REDACTED]

■ [REDACTED]

■ [REDACTED]

■ [REDACTED]

■ [REDACTED]

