### 3.3 PHASE II (PART 2) STUDY DESIGN

Phase II (Part 2) of this study is a multi-center, double-blind, randomized, vehicle-controlled study of the safety and efficacy of topically applied AMTX-100 *CF3* in adult patients with Mild to Moderate AD. Sixty (60) subjects will be enrolled in 2 groups of AMTX-100 *CF3* and placebo (vehicle). The subjects will be randomized in a 1:1 ratio, thus thirty (30) subjects will be randomized in each group (Group A: Treatment 1.1% w/w of AMTX-100 *CF3*) and Group B: placebo (vehicle 0% w/w)). Each enrolled subject, after screening and randomization, will receive AMTX-100 *CF3* 1.1% w/w or placebo (vehicle) to be applied twice daily to all treatable AD lesions (excluding the scalp, face, eyes, eyelids, hands, palms, feet, groin, genitals or in the axillae) for 28 consecutive days.

The study groups are as follows:

- **Group A:** AMTX-100 *CF3* dose concentration (1.1% w/w), topically applied twice a day for 28 consecutive days to all treatable AD affected areas
- **Group B:** Placebo (Vehicle) (0% w/w), topically applied twice a day for 28 consecutive days to all treatable AD affected areas

[REDACTED]

[REDACTED]

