### **3.5.5 PHASE II (PART 2) INCLUSION CRITERIA**

Subjects are required to meet ALL of the following criteria for randomization into the Phase II (Part 2) of the study:

1. Male or female subjects who are 18 years or older.
2. If female and not infertile (defined below), the subject must agree for the duration of the study to use one of the following forms of contraception 1) systemic hormonal treatment 2) an intrauterine device (IUD) which was implanted at least 2 months prior to screening or 3) "double-barrier" contraception (condom, diaphragm and spermicide are each considered a barrier). Females are considered to be infertile if they are either a) surgically sterile or b) have had spontaneous amenorrhea for at least the last 2 years and at least 2 years after the onset of amenorrhea while not receiving hormone replacement therapy.
3. All fertile female subjects as described above need to have a negative urine pregnancy test at the screening and baseline visits.
4. Subject is capable of providing informed consent and is willing to sign the ICF prior to study Screening and agrees to comply with the study protocol requirements.
5. Subject is able to apply topical products on all the treatable areas by self and/or caregiver (if applicable), per the Investigator.
6. Subject is willing and able to comply with all clinic visits and study-related procedures.
7. Subject is able to understand and complete study-related questionnaires.

8. The subject has physician confirmed mild to moderate Atopic Dermatitis (AD) defined by the Eichenfield revised criteria of Hannifin and Rajka, for at least 6 months prior to study enrollment.
9. Validated Investigator's Global Assessment for Atopic Dermatitis (vIGA-AD™) score of 2 or 3 (mild to moderate) at the screening and baseline visits.
10. Eczema Area and Severity Index (EASI) score lower than 23 at the screening and baseline visits
11. Subject has Atopic Dermatitis (AD) involvement between 5% and 30% treatable BSA (excluding the scalp, face, eyes, eyelids, hands, palms, feet, groin, genitals or in the axillae) appropriate for topical treatment at the screening and baseline visits.

*Note: Calculation of Treatable BSA percentage (% of the total BSA that is AD-involved, excluding the scalp, face, eyes, eyelids, hands, palms, feet, groin, genitals or in the axillae) will be completed by Rule of Nines method:*

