### **3.5.6 PHASE II (PART 2) EXCLUSION CRITERIA**

Subjects are required to meet NONE of the following criteria for randomization into the Phase II (Part 2) of the study:

1. Pregnant or lactating females or women who are planning for pregnancy in the next 6 months
2. Women at postpartum for 3 months or less prior to screening
3. Serious medical illnesses such as end-stage renal disease, liver failure or heart failure that, in the opinion of the Investigator may interfere with the conduct of the study
4. Subjects with abnormal vital signs, physical and dermatological exams or clinical laboratory evaluations considered clinically significant by the Principal Investigator, which in the opinion of the PI would significantly interfere with the study conduct
5. Subjects with any concurrent skin condition that could interfere with the evaluation of the treatment areas, as determined by the investigator
6. The subject has a planned major surgical intervention for a pre-existing condition within the duration of the study
7. The subject has a history of drug or alcohol abuse that would impair or risk the subject's full participation in the study, in the opinion of the investigator.

8. Participation in a clinical trial within 3 months, or more than two clinical trials within 12 months prior to screening
9. Concurrent or recent use of prescription moisturizers, topical steroids, topical immunosuppressive/immunomodulative drugs, topical vitamin D3 derivative, topical retinoids, anthralin, coal tar (except when used as shampoo) or salicylic acid within 14 days of the baseline visit
10. The subject has severe AD as determined by vIGA-AD™ score higher than 3
11. The subject cannot avoid systemic treatments (including systemic corticosteroids, immunotherapy, biologics or phototherapy) for AD during the study per the Investigator
12. The subject has previously received any systemic treatments, immunotherapy, biologics or phototherapy for AD within 12 months prior to study enrollment
13. Current or expected use of prohibited medications and procedures during study treatment, as described in [Section 7](#), unless approved by the study Medical Monitor
14. Subject has unstable AD or any consistent requirement for high-potency topical corticosteroids to manage AD signs and symptoms
15. Subject has a significant active systemic or localized infection, including known actively infected AD

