## 6 STUDY TREATMENTS

### 6.1 METHOD FOR ASSIGNING ELIGIBLE SUBJECTS TO TREATMENT

In Part 1 of the study, study eligible subjects will be assigned to open-label AMTX-100 CF (in 1.1% concentration), based on a cohort assignment schedule prepared by the contracted CRO. Details of the cohort assignment and assignment of the subject number are provided in [Section 8.11](#) and [Section 4.1.1](#).

Subjects in Part 1 of the study will be assigned sequentially to one of the following treatment groups:

█ [REDACTED]

█ [REDACTED]

█ [REDACTED]

█ [REDACTED]

█ [REDACTED]

After a subject has been determined to be eligible for the treatment in Part 1 of the study, a cohort assignment number will be assigned. Once the cohort assignment number is assigned, it cannot be re-assigned even if the subject is subsequently deemed ineligible or withdraws consent.

[REDACTED]

In Part 2 of the study, study eligible subjects will be randomized based on a randomization schedule prepared by the contracted CRO. Details of the randomization and assignment of the subject number are provided in [Section 8.12](#) and [Section 4.2.1](#).

Subjects will be randomized in a 1:1 ratio to one of the following treatment groups in Part 2 of the study:

- Active Treatment (Group A): AMTX-100 CF3 (1.1% w/w);
- Placebo (Group B): Vehicle ( 0% w/w)

After a subject has been determined to be eligible for the treatment in the study, a randomization number will be assigned. Once the randomization number is assigned, it cannot be re-assigned even if the subject is subsequently deemed ineligible or withdraws consent.

[figure not shown]

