### 9.4 RANDOMIZATION

There is no randomization for the Phase I (Part 1) of the study. In Phase II (Part 2) of the study, subjects will be randomized using a web-based randomization system at Visit 2 and site personnel will be trained on this system. Only those subjects who successfully complete the screening phase and meet the study eligibility criteria will proceed to randomization. The randomized subjects will receive study treatment at the assigned doses for 28 consecutive days (56 applications in total) and followed up for 2 weeks to assess post-treatment safety.

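### Should Part 2 randomisation be stratified by baseline vIGA-AD grade, given that a grade-2 entrant responds only at score 0?

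*Protocol*

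**What the plan says.** **Endpoint.** Protocol 9.2.2.1 requires both parts of a composite at Day 28: a vIGA-AD "score of 0 (clear) or 1 (almost clear) (on a 5-point scale) and a reduction of" 2 points or more. Subjects given rescue treatment count as non-responders.

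**Entry.** Section 3.5.5 item 9 admits a "score of 2 or 3 (mild to moderate) at the screening and baseline visits". Section 3.5.6 item 10 shuts out higher grades: "The subject has severe AD as determined by vIGA-AD™ score higher than 3".

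**Allocation.** Section 3.3 gives a 1:1 ratio, "thus thirty (30) subjects will be randomized in each group". Section 6.1 says that "study eligible subjects will be randomized based on a randomization schedule prepared by the contracted CRO" and refers to 8.12 for the details. The readable part of 8.12 says that "subjects will be randomized using a web-based randomization system at Visit 2 and site personnel will be trained on this system", and blacked-out blocks follow. Section 9.4 repeats that sentence and adds that "Only those subjects who successfully complete the screening phase and meet the study eligibility criteria will proceed to randomization". None of these names a stratification factor of any kind.

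**Analysis.** Section 9 announces "general information about statistical considerations and concepts such as randomization, covariates, statistical power, sample size" and leaves detailed methods to a SAP. The contents page lists a section 9.10 on covariates and prognostic factors, but its text is blacked out, as are much of 9.12 and the method list in 9.14. SAP section 1 limits that document to Part 1. Its section 2.3, on randomisation and stratification, says only that Part 1 is not randomised.

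**The concern.** The same responder rule sets a different target by entry grade. Someone entering at 3 succeeds by reaching almost clear; someone entering at 2 must clear completely. If that makes response easier from one grade than from the other, the mix of grades in each arm affects the observed response rates.

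With only 30 per arm, chance alone can leave the arms unequal in grade. Randomisation still protects the comparison on average, but in the single trial actually run, part of the observed difference could be case mix. The factor has two levels and is scored before randomisation for eligibility, so stratifying looks nearly free. Section 9.4 carries no blacked-out text and does not mention it, which reads at first like an omission.

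**Working it through.** **1. Responder states by entry grade.** The score must be 0 or 1 and baseline minus score must be at least 2.
- Baseline 3: 3 - 0 = 3 and 3 - 1 = 2. Both 0 and 1 qualify.
- Baseline 2: 2 - 0 = 2 qualifies; 2 - 1 = 1 does not. Only 0 qualifies.

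Both grades need a fall of two grades or more, to different end states. The documents give no response or transition rates by grade, so neither the direction nor the strength of any prognostic effect can be derived from them.

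**2. Arm size.** 60 / 2 = 30, as section 3.3 states. Section 9.3 says that 60 was chosen by clinical judgment, so there is no power figure to reproduce.

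**3. Chance imbalance without stratification.** Let K of the 60 subjects be at grade 3 and X of them fall in one arm of 30 (hypergeometric). The gap in grade-3 share is (2X - K)/30, with SD = (2/30) x sqrt[30 x (K/60) x (1 - K/60) x (30/59)].
- K = 30: (2/30) x sqrt(3.814) = 0.130.
- K = 18 or 42: (2/30) x sqrt(3.203) = 0.119.

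The exact probability of a gap of at least 6 of 30 (20 points), in either direction, is 0.158 for K = 18, 0.196 for K = 30 and 0.158 for K = 42. Half of each favours active: 7.9% to 9.8% of trials.

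**4. Shift from a gap of exactly 20 points.** With no drug effect, shift = 0.20 x (response at grade 3 - response at grade 2). The rates are assumptions. The error rates come from 600,000 simulated trials per scenario, using a crude pooled z-test at one-sided 2.5%. They apply to gaps of 20 points or more in favour of active.

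| Assumed response, grade 3 v grade 2 | Shift (points) | Crude false-positive rate | Cochran-Mantel-Haenszel (CMH) by grade |
|---|---|---|---|
| 30-40% v 5% | 5 to 7 | 6.5-11.1% | 2.2-2.5% |
| 20% v 10% | 2 | 4.0-4.7% | 2.2-2.3% |
| 15% v 10% | 1 | 3.5-3.7% | not given |

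In the first row the standard error of the difference is 8.6-11.8 points, larger than the shift. When the gap favours vehicle, the crude rate in that row is 0.1-0.5%. The two directions offset each other: over all trials the crude test's false-positive rate is 2.4-2.8%.

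Even in the worst case shown, a large gap favouring active together with a false positive arises in at most 0.098 x 0.111 = 1.1% of trials.

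**5. With a drug effect.** Assume 35-40% v 15% at grade 3 and 10-12% v 3-4% at grade 2. A 20-point gap shifts the difference by 3.7-3.9 points. Power is 44-63% when a gap of 20 points or more favours active and 13-31% when it favours vehicle.

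Averaged over all trials:
- Stratified allocation plus CMH gains 0.6-2.4 points of power, or 0.1-0.4 if grade is barely prognostic.
- CMH without stratified allocation changes power by -0.9 to +1.7 points, and loses 0.6-1.5 points if grade is barely prognostic.

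**6. Where a factor or covariate could already stand.** Section 9.4 is readable and silent, but it does not give the 1:1 ratio either; that is in 3.3 and 6.1. It is therefore not the full allocation specification. The section named as holding the details, 8.12, is followed by blacked-out blocks, as is the randomisation text in the synopsis. Section 9.10 and the 9.14 method list are hidden. The protocol's abbreviation list includes analysis of covariance, yet no readable section uses it. That suggests a covariate-adjusted model in hidden text, though not that the binary primary endpoint is adjusted.

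**The case for a change.** The best case for acting is that this is one small trial with a binary primary endpoint and no power calculation, so nothing readable shows room to absorb imbalance. Roughly one run in six to one in five would carry a 20-point gap, and a reader could not then separate case mix from drug effect without an adjusted analysis or response by grade. Section 9.14 makes the efficacy evaluable population primary and 9.9 rules out imputation, so losses after randomisation could disturb the balance further. The score is already collected, and the request could be made conditional on what the hidden text says.

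The responder arithmetic and the imbalance probabilities stand. It is also fair to ask the sponsor whether baseline grade is already a factor or covariate, and to expect response by baseline grade to be tabulated.

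The rest is weaker:
- Silence beside blacked-out text does not show that the plan lacks stratification.
- The largest error rates need both a gap of at least 20 points in one direction and response 6 to 8 times higher at grade 3 than at grade 2 (30/5 = 6, 40/5 = 8). Every scenario assumes that grade 3 is the easier responder.
- No Part 2 alpha, sidedness or test is readable, so these error rates and powers describe an assumed test.
- The simulated gain assumes exactly equal grade counts per arm. If allocation were also blocked by centre, up to 20 centres x 2 grades = 40 strata would share 60 subjects, 1.5 each, and incomplete blocks would leave some imbalance.
- If randomisation has begun, the fallback of adjusting alone may lose power.

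**Conclusion.** No change to the plan follows. The endpoint sets different target states for the two entry grades, so baseline grade may be prognostic. That is a property of a coherent definition, and the documents do not settle the direction or the strength of the effect. The supposed gap cannot be shown: the allocation details, the covariates section and the Part 2 methods are wholly or partly blacked out, and no Part 2 SAP is supplied.

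If allocation is in fact unstratified, there is no average bias and the overall false-positive rate is 2.4-2.8% against a nominal 2.5%. Stratified allocation with a matching test would add 0.1-2.4 points of average power. These figures rest on an assumed grade-3 share of 30-70%, assumed response rates and an assumed one-sided 2.5% test.

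What remains is a question for the sponsor and a routine descriptive table of response by baseline grade, which analysts can supply without altering the design.

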#### 9.2.2.4 Safety Outcome Measures

- Incidence of Treatment-Emergent Adverse Events (TEAE)
- Incidence of withdrawals from the study due to TEAEs
- Changes from baseline in study treatment application site reaction assessment
- Changes and shifts in laboratory measurements over time
- Changes in vital signs over time

### 9.3 SAMPLE SIZE DETERMINATION AND RATIONALE

**Sample size for Phase I (Part 1):** The sample size of 25 subjects (5 subjects per cohort) for Phase I of this study is selected on the basis of clinical judgment and not based on statistical power calculation. The number of subjects is deemed adequate to provide clinically meaningful descriptive results consistent with study objectives.

**Sample size for Phase II (Part 2):** The sample size of 60 subjects for Phase II of this study is selected on the basis of clinical judgment and not based on statistical power calculation. The number of subjects is deemed adequate to provide clinically meaningful results consistent with study objectives.

### 9.4 RANDOMIZATION

There is no randomization for the Phase I (Part 1) of the study. In Phase II (Part 2) of the study, subjects will be randomized using a web-based randomization system at Visit 2 and site personnel will be trained on this system. Only those subjects who successfully complete the screening phase and meet the study eligibility criteria will proceed to randomization. The randomized subjects will receive study treatment at the assigned doses for 28 consecutive days (56 applications in total) and followed up for 2 weeks to assess post-treatment safety.

